#### **2.4.2 Prior, concomitant and post therapies**

Concomitant therapies will be coded using the WHO Drug Reference List dictionary that employs the WHO Anatomical Therapeutic Chemical (ATC) classification system and summarized by lowest ATC class and preferred term using frequency counts and percentages. Surgical and medical procedures will be coded using MedDRA and summarized by SOC and preferred term. These summaries will include therapies starting on or after the start of study treatment but no later than 30 days after last dose of study treatment or therapies starting prior to the start of study treatment and continuing after the start of study treatment.

All therapies will be listed. Any therapy starting and ending prior to the start of study treatment or starting more than 30 days after the last date of study treatment will be flagged in the listing as prior or post therapies respectively. Those starting or continuing on or after the start date of study treatment and up to 30 days after the last date of study treatment will be flagged as concomitant therapies in the listing. The safety set will be used for all therapies tables.

#### **2.5 Analysis of the primary objective**

The primary objective of the study is to evaluate the efficacy of eltrombopag in combination with r-ATG and CsA in terms of CR rate at Week 26 in the treatment-naïve East-Asian patients with SAA.

All analysis for primary endpoint including supplementary analysis, supportive analysis and subgroup analysis will not be reproduced in final analysis.

### **2.5.1 Primary endpoint**

The primary efficacy endpoint is CR rate at Week 26 (6 months), which is defined as the percentage of all subjects who meet the hematological criteria of CR at Week 26. A complete response (CR) is defined as meeting all the following 3 criteria on 2 consecutive serial blood count measurements at least one week apart but not more than 4 weeks apart.

A CR will be defined as (all 3 must be met):

- Absolute neutrophil count  $> 1.0 \times 10^9/L$
- Platelet count  $> 100 \times 10^9/L$
- Hemoglobin  $> 100 \text{ g/L}$

The primary endpoint will be based on the investigator assessment of response. However, improvement in counts that are dependent upon exogenously administered growth factors or transfusion will not be considered as fulfilling response criteria.

The exclusion period of these therapies are detailed below:

- Platelets transfusions: 7 days preceding the assessment of platelet count
- Packed RBC transfusions: 14 days preceding the assessment of hemoglobin
- Growth factors: 21 days preceding the assessment of response

The analysis of the primary efficacy endpoint will be based on the FAS.

### **2.5.2 Statistical hypothesis, model, and method of analysis**

The CR at Week 26 will be summarized using point estimate and 2-sided exact binomial 95% ([Clopper-Pearson](#)) confidence intervals.

### **2.5.3 Handling of missing values/censoring/discontinuations**

Subjects who are not evaluable for response at Week 26 for any reason, including missing data and withdrawal from the study before Week 26, will be treated as non-responders in the primary analysis.

### **2.5.4 Supplementary analyses**

The CR will also be derived programmatically using laboratory results (criteria details are stated in the [section 2.5.1](#) ) instead of those reported by the investigators in the response assessment CRF. The response will be derived if two consecutive serial blood count measurements meet the defined requirements, where one of the measurements is done at Week 26. The derived response will be listed against investigator assessment of response and discrepancies will be identified with justifying comment, when available.

### **2.5.5 Supportive analyses**

Supportive analyses using the CR at Week 26 will be generated per programmatically derived in the following way:

A more stringent definition of CR meeting all the following criteria on 2 consecutive serial blood count measurements at least one week apart:

- Normal hemoglobin concentration for age and gender
- PLT  $>150 \times 10^9/L$
- Absolute neutrophil count (ANC)  $>1.5 \times 10^9/L$

Since this is a more stringent definition of CR, very few CRs will be expected for analysis.

### **Subgroup analyses for the primary endpoint**

The primary efficacy endpoint and supportive analyses (more stringent definition of CR) will be summarized by the above subgroups listed in [section 2.2.1](#) for efficacy. The proportion of the complete response in each subgroup will be summarized using point estimates and 95% exact ([Clopper-Pearson](#)) confidence intervals.

In addition, hematological responses will be listed.

### **2.6 Key secondary endpoint**

Not applicable

### **2.7 Analysis of secondary efficacy objective(s)**

The secondary objectives in this study are:

- To evaluate complete response rate at 3, 12 months and yearly after;
- To evaluate overall response rate at 3, 6, 12 months and yearly after;
- To evaluate duration of response;
- To evaluate overall survival;
- To evaluate the need for transfusion (packed RBC units and platelet units);
- To evaluate the safety and tolerability of eltrombopag in combination with r-ATG and CsA;
- To evaluate clonal evolution;
- To determine the PK of eltrombopag in East-Asian treatment naive SAA patients.

All analysis will not be reproduced in final analysis for secondary endpoints which are at or prior to Week 26. These include CR rate at Week 13, overall response (CR+PR) rate at Week 13 and Week 26, time to response, transfusion-free interval at Week 13 and Week 26, transfusion frequency and amount at Week 13 and Week 26, changes in platelet count, hemoglobin and neutrophil count at Week 13 and Week 26.

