##### **Overall response (CR+PR) rate at Week 13, Week 26, Week 52 and yearly after**

Hematologic overall response rate at specific visit is defined as percentage of subjects who achieved hematologic response by investigator assessment at specific visit in FAS.

The overall hematological response is defined as either complete or partial response. CR is defined in [section 2.5.1](#).

Partial response (PR) is defined as blood counts no longer meeting the standard criteria for severe pancytopenia in SAA, equivalent to at least 2 of the 3 criteria below, but are not sufficient for a CR.

- Absolute neutrophil count  $\geq 0.5 \times 10^9/L$
- Platelet count  $\geq 20 \times 10^9/L$
- Reticulocyte count  $\geq 20 \times 10^9/L$

However, improvement in counts that are dependent upon exogenously administered growth factors or transfusion will not be considered as fulfilling response criteria.

The exclusion period of these therapies are detailed below:

- Platelets transfusions: 7 days preceding the assessment of platelet count
- Packed RBC transfusions: 14 days preceding the assessment of hemoglobin
- Growth factors: 21 days preceding the assessment of response.

Of note that the criteria for complete and partial responses must be met on 2 consecutive serial blood count measurements at least one week apart but not more than 4 weeks apart for the Week 13 and Week 26 assessments but only on one blood count measurements for the yearly assessments thereafter.

Patients who relapse or withdraw from the study will be counted and reported as relapsed or withdrawn for all subsequent response assessments. No response (NR) is defined as not fulfilling the response criteria.

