### **Time to response**

Time to response is defined as the time from the date of the start of study treatment until the first documented and confirmed response (either CR or PR) per programmatically derived.

Time to complete response is similarly defined as the time from the date of the start of study treatment until the first documented complete response.

All subjects in the FAS will be included in the time to response/CR calculations.

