### **Time to response**

The Kaplan-Meier curve of the time to response and time to complete response will be constructed, and the quartiles of the survival function will be provided along with 95% confidence interval. Kaplan-Meier estimates with 95% confidence intervals every 3 months will be summarized as well.

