### **Time to response**

For time to response and time to complete response, if a subject does not meet response/CR before or at the cutoff date, censoring will be performed using the date of the last response assessment.

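### The final-analysis SAP puts time to response on its Week 26 not-rerun list, which in effect freezes time to complete response although a first CR after Week 26 still counts

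*SAP*

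**What the plan says.** The SAP file holds two plans, one for the primary analysis (revised 1-Jul-2022) and one for the final analysis (11-Nov-2024). The point concerns the second.

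- **Section 2.7, rule.** "All analysis will not be reproduced in final analysis for secondary endpoints which are at or prior to Week 26".
- **Section 2.7, list.** "These include CR rate at Week 13, overall response (CR+PR) rate at Week 13 and Week 26, time to response", followed by transfusion and blood-count items. Time to response is the only item without a Week 13 or Week 26 label.
- **Section 2.7.1, Time to response.** Two endpoints stand under this heading: time to first response (CR or PR), and time to complete response, which runs "until the first documented complete response". Neither has an upper time limit. On population: "All subjects in the FAS will be included in the time to response/CR calculations".
- **Section 2.7.3, censoring.** A participant is censored at the last response assessment "if a subject does not meet response/CR before or at the cutoff date". The final plan sets that cut-off at the end of the study.
- **Section 2.7.1, Overall response.** Two confirming counts are needed at Weeks 13 and 26, "but only on one blood count measurements for the yearly assessments thereafter". Response status is therefore still assessed after Week 26.
- **Section 4.** The primary-analysis SAP names time to response among the endpoints added beyond the protocol. The final-analysis SAP drops it from the same list.

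Duration of response, including duration of complete response, and the CR rates at Week 52 and yearly are not on the not-rerun list.

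**The concern.** The reason given for not rerunning an endpoint is that it is complete by Week 26. Time to complete response does not fit that reason. Under Protocol Section 3, participants in CR or PR at Week 26 may continue eltrombopag to Week 52 and CsA beyond that. Under Protocol Section 8.3, their blood counts continue every 2 to 4 weeks until eltrombopag ends and yearly to Year 3. A Week 26 partial responder can therefore have a first CR that the definition counts.

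At stake is the consistency of the final report. Duration of CR starts at the event that ends time to CR. If one is updated and the other is not, some participants will have a CR duration while the only time-to-CR curve shows them as never having reached CR.

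**Working it through.** **1. The plan's own figure.** SAP Section 3.1 expects a CR rate of 44.0% in 36 participants: 0.44 × 36 = 15.84, taken as 16. For 16/36 = 44.4%, the Clopper-Pearson limits are 27.9% and 61.9%, as in Table 3-1. Only the 16 is used below.

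**2. Earliest primary cut-off.** Last patient first visit was 03-Dec-2021 (Protocol, Amendment 3 rationale). Screening lasts up to 30 days (Protocol 8.1), so the last Day 1 lies between 03-Dec-2021 and 02-Jan-2022. The cut-off follows completion of Week 26 by all (primary-analysis SAP 2.1). Adding 182 days gives 03-Jun-2022 to 03-Jul-2022. The documents do not give the actual date.

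**3. Follow-up at that cut-off.** No participant was enrolled by 16-Jun-2020, and three by 08-Dec-2020 (Amendments 1 and 2).

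| Milestone | Day 1 needed by (cut-off minus milestone) | Reached |
|---|---|---|
| Week 156 (1092 days) | 07-Jun-2019 to 07-Jul-2019 | 0 of 36 |
| Week 104 (728 days) | 05-Jun-2020 to 05-Jul-2020 | at most 3 of 36 |
| Week 52 (364 days) | 04-Jun-2021 to 04-Jul-2021 | not fixed by the documents |

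The fourth participant was enrolled on 09-Dec-2020 at the earliest and could not reach Week 104 before 07-Dec-2022.

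For Week 52, if the remaining 33 enrolled evenly over the 360 days from 08-Dec-2020 to 03-Dec-2021, the number still short of it is 33 × 182/360 = 16.7, about 17. Without that assumption, the number lies anywhere from 1 to 33.

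**4. Who could still have a first CR.** Participants already in CR have had the event. Under Protocol Section 3, efficacy assessment stops at no response at Week 26, at relapse and at alternative treatment. That leaves mainly the Week 26 partial responders: 36 × overall response rate − 16. The rates below come from Protocol Section 1.1 and are assumptions for this trial, because they describe r-ATG/CsA without eltrombopag.

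| Overall response assumed | Responders | Minus 16 CRs = partial responders |
|---|---|---|
| 50% | 18.0 | 2 |
| 58% | 20.9 | about 5 |
| 70% | 25.2 | about 9 |

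These are ceilings for the CRs missed. Anyone who converted between Week 26 and the primary cut-off is already in the curve.

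**5. Illustration only.** If 25% to 50% of them converted (assumed; the documents give no rate), the number ever in CR would rise from 16/36 = 44.4% to between 16.5/36 = 45.8% (2 partial responders, 25%) and 20.5/36 = 56.9% (9 partial responders, 50%). Only conversions after the primary cut-off would be missing from the curve.

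**6. One participant traced through the final report.** Take a Week 26 partial responder who first reaches CR after the primary cut-off and is still in CR at the next yearly visit.

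| Analysis | Rerun? | How this participant appears |
|---|---|---|
| Time to CR | No | Censored at the last response assessment before the primary cut-off |
| Duration of CR | Yes | Included, starting at the first CR |
| Yearly CR rate | Yes | Counted as CR at that visit |

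The first two rows disagree about whether the participant ever reached CR.

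**The case against.** **The list does not name time to complete response.** Section 2.7 names only time to response, while Sections 2.7.2 and 2.7.3 name the two endpoints separately. Read literally, time to CR would still be run. This is a fair point of wording. Against it, both endpoints stand under the one heading that the list uses, and Section 4 drops the item altogether. The likelier reading is that neither is rerun.

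**The classification is right for the endpoint that is named.** A reader might infer that both endpoints are wrongly frozen. The documents do not support that. Week 26 non-responders leave efficacy assessment, so first responses of either kind are essentially all seen by Week 26. This stands.

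**The methods text is retained by convention.** Section 2.7.2 still says "The Kaplan-Meier curve of the time to response and time to complete response will be constructed". A reader might take this as a second, contradictory instruction. Section 2.5 likewise keeps full methods for a primary endpoint that it says will not be reproduced, so the retained text proves little. The case rests on the definition and the censoring rule.

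**Late CRs are reported elsewhere.** The Week 52 and yearly CR rates are kept, and responses are listed. So late CRs are not lost to the report. But a visit-specific rate gives the proportion in CR on that date, not the time to first CR or the proportion ever in CR.

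**First-CR dates become coarse.** Once eltrombopag ends, scheduled counts are yearly. This limits what an update adds after Week 52, but not between Week 26 and Week 52, when counts are every 2 to 4 weeks.

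**Conclusion.** The point holds for time to complete response and not for time to first response. The final-analysis SAP treats as closed at Week 26 an endpoint that its own definition leaves open, and it updates the linked duration of CR without updating time to CR.

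The size is modest. About 2 to 9 of 36 participants could still have had a first CR after Week 26, on the assumptions of 16 CRs and 50% to 70% overall response. The endpoint is descriptive, was added by the SAP, and bears on no test or primary conclusion.

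Three stronger readings are tempting but unsupported:

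- **That about 17 of 36 are lost.** That figure counts participants short of Week 52 under even accrual, and most of them would already be in CR or no longer assessed.
- **That nobody could have reached Year 2.** If the cut-off fell in mid-June 2022 or later, up to three might have.
- **That the frozen curve is biased.** Participants without CR are censored in a Kaplan-Meier analysis. What the documents show is shorter follow-up and lower precision.

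**What to change.** In Section 2.7 of the final-analysis SAP, limit the listed item to time to first response (CR or PR), and state that time to complete response will be rerun at the final cut-off. Restore time to complete response to the added endpoints in Section 4. Time to first response can stay as reported at the primary analysis.

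The cost is one phrase in each section and a rerun of existing programs. The first-CR dates have to be derived for duration of CR in any case. If the final report is already written, label the existing curve with its primary cut-off date and add the updated one.

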#### **2.7.1 Secondary efficacy endpoints**

##### **CR rate at Week 13, Week 52 and yearly after**

CR rate at specific visit is defined as percentage of subjects who meet the hematological CR criteria by investigator assessment at Week 13, Week 52 and yearly after respectively in FAS. See [Section 2.5.1](#) for definition of CR.

##### **Overall response (CR+PR) rate at Week 13, Week 26, Week 52 and yearly after**

Hematologic overall response rate at specific visit is defined as percentage of subjects who achieved hematologic response by investigator assessment at specific visit in FAS.

The overall hematological response is defined as either complete or partial response. CR is defined in [section 2.5.1](#).

Partial response (PR) is defined as blood counts no longer meeting the standard criteria for severe pancytopenia in SAA, equivalent to at least 2 of the 3 criteria below, but are not sufficient for a CR.

- Absolute neutrophil count  $\geq 0.5 \times 10^9/L$
- Platelet count  $\geq 20 \times 10^9/L$
- Reticulocyte count  $\geq 20 \times 10^9/L$

However, improvement in counts that are dependent upon exogenously administered growth factors or transfusion will not be considered as fulfilling response criteria.

The exclusion period of these therapies are detailed below:

- Platelets transfusions: 7 days preceding the assessment of platelet count
- Packed RBC transfusions: 14 days preceding the assessment of hemoglobin
- Growth factors: 21 days preceding the assessment of response.

Of note that the criteria for complete and partial responses must be met on 2 consecutive serial blood count measurements at least one week apart but not more than 4 weeks apart for the Week 13 and Week 26 assessments but only on one blood count measurements for the yearly assessments thereafter.

Patients who relapse or withdraw from the study will be counted and reported as relapsed or withdrawn for all subsequent response assessments. No response (NR) is defined as not fulfilling the response criteria.

### **Time to response**

Time to response is defined as the time from the date of the start of study treatment until the first documented and confirmed response (either CR or PR) per programmatically derived.

Time to complete response is similarly defined as the time from the date of the start of study treatment until the first documented complete response.

All subjects in the FAS will be included in the time to response/CR calculations.

### **Duration of response**

Duration of response will be derived as the time from first documented and confirmed response (either CR or PR) until the time of relapse or death whichever occurs first. Both the responses and the relapse will be programmatically derived. Patients who are neither complete nor partial responders will not be included in the analysis of the duration of response.

Duration of complete response will be similarly derived for patients who had a complete response. Patients who are not complete responders will not be included in the analysis of the duration of complete response.

Clinical relapse is considered as the occurrence of any of the following event in a subject who had achieved a hematological response (CR or PR) but has subsequently lost response (not

explained by any other independent concomitant medical conditions) in one blood count measurements:

- meeting again the criteria for SAA, equivalent to patients with at least two of the following parameters in peripheral blood.
  - Absolute neutrophil count  $< 0.5 \times 10^9/L$
  - Platelet count  $< 20 \times 10^9/L$
  - Absolute reticulocyte count  $< 20 \times 10^9/L$
- requirement for transfusion again for subjects who had been transfusion independent
- decrease in any of the peripheral blood counts to: absolute neutrophil count  $< 0.5 \times 10^9/L$  or platelets  $< 20 \times 10^9/L$ .

The analysis of duration of response will be based on response assessment which are derived programmatically using laboratory results instead of those reported in the response assessment CRF.

### **Transfusion-free interval before Week 13 and Week 26**

For platelet transfusion, transfusion-free interval is defined as the time from most recent platelet transfusion preceding response assessment to the date of response assessment. For RBC transfusion, transfusion-free interval is defined as the time from most recent RBC transfusion preceding response assessment to the date of response assessment.

### **Maximum duration of Platelet and RBC transfusion free**

Transfusion free duration will be defined as the period from the next day after transfusion to the day of the next transfusion. Maximum duration of platelet and RBC transfusion free for each subject will be picked for analysis.

### **Proportion of subjects who become transfusion independent**

The number and percentage of subjects with platelet or RBC transfusion independence during the study will be presented respectively. This analysis will be performed for the subgroup of subjects with baseline transfusion dependence.

Post-baseline transfusion independence is defined as follows:

- Platelet transfusion independence: The subjects who are transfusion dependent at baseline become transfusion free for a period of at least 4 weeks after baseline.
- RBC transfusion independence: The subjects who are transfusion dependent at baseline become transfusion free for a period of at least 8 weeks after baseline.

### **Transfusion frequency and amount (units)**

For subjects receiving platelet transfusion at baseline, the frequency and the amount of platelets transfusion in each period (Baseline: 4 weeks before Day 1; Week 13, 26, 52 and Yearly thereafter: 4 weeks before each visit day) will be summarized. The same analysis applies to RBC transfusion (period will be extended to 8 weeks). The amount of transfusion will be defined as the sum of units of transfusion.

Subjects with platelet transfusion decrease is defined as subjects with transfusion decrease or transfusion free in each period (Week 13, 26, 52 and Yearly thereafter: 4 weeks before each

visit day) compared to baseline (Baseline: 4 weeks before Day 1). 50% platelet transfusion reduction is defined as subjects with transfusion decrease of amount (units) at least 50% compared to baseline. The same analysis applies to RBC transfusion (period will be extended to 8 weeks). The number and percentage of subjects with platelet or RBC transfusion decrease and 50% platelet transfusion reduction in each period will be presented.

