- Platelet transfusion independence: participants who did not receive platelet transfusions in the 4 weeks before Day 1.
- Platelet transfusion dependence: participants who received one or more platelet transfusions in the 4 weeks before Day 1.

Baseline RBC transfusion independence/dependence are defined as:

- RBC transfusion independence: participants who did not receive RBC transfusions in the 60 days before Day 1.
- RBC transfusion dependence: participants who received one or more RBC transfusions in the 60 days before Day 1.

Investigators will have the discretion to record abnormal test findings on the appropriate CRF whenever, in their judgment, the test abnormality occurred prior to the informed consent signature.

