#### **Transfusion frequency and amount**

The frequency and the amount of platelets and RBC transfusion in each period will be summarized by descriptive statistics including mean, SD, median, 25th and 75th percentiles, minimum, and maximum.

The number and percentage of subjects with platelet or RBC transfusion decrease and 50% platelet transfusion reduction in each period will be presented.

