### **Transfusion frequency and amount**

The transfusion frequency and amount and the proportion of subjects with transfusion decrease will be only performed for the subgroup of subjects with baseline transfusion dependent.

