### 4 Change to protocol specified analyses

Below-listed endpoints were added to further support efficacy analysis beyond protocol.

- Maximum duration of Platelet and RBC transfusion free
- Proportion of subjects with transfusion decrease
- Changes in platelet count, hemoglobin and neutrophil count

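### The transfusion-decrease measure in both SAPs counts any fall from one baseline window in already-transfused participants, with no per-participant count of unchanged or increased need

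*SAP*

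**What the plan says.** The primary-analysis SAP and the final-analysis SAP use the same text in Sections 2.7.1 to 2.7.3.

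- **Definition (2.7.1).** "Subjects with platelet transfusion decrease is defined as subjects with transfusion decrease or transfusion free in each period", compared with the baseline window. No minimum fall is given, and the text does not say whether number of transfusions or units is compared.
- **Windows (2.7.1).** Platelets use the 4 weeks before Day 1 and the 4 weeks before each visit. For red cells, "The same analysis applies to RBC transfusion (period will be extended to 8 weeks").
- **Companion row (2.7.1).** "50% platelet transfusion reduction is defined as subjects with transfusion decrease of amount (units) at least 50% compared to baseline". This row is explicitly in units.
- **Population (2.7.3).** Transfusion frequency and amount and "the proportion of subjects with transfusion decrease will be only performed for the subgroup of subjects with baseline transfusion dependent".
- **Dependence (Protocol 8.2).** "Platelet transfusion dependence: participants who received one or more platelet transfusions in the 4 weeks before Day 1". For red cells the look-back is 60 days.
- **Per-participant output (2.7.2).** "The number and percentage of subjects with platelet or RBC transfusion decrease and 50% platelet transfusion reduction in each period will be presented". No unchanged or increased category appears.
- **Group output (2.7.2).** "The frequency and the amount of platelets and RBC transfusion in each period will be summarized by descriptive statistics including mean, SD, median", with quartiles, minimum and maximum.
- **Status (Section 4).** "Proportion of subjects with transfusion decrease" is listed among the endpoints added beyond the protocol in support of efficacy.

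The final-analysis SAP (2.7) does not repeat the Week 13 and Week 26 transfusion summaries, so there the measure applies at Week 52 and yearly. Weeks 13 and 26 fall under the primary-analysis SAP.

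**The concern.** Transfusion counts vary from one window to the next even when underlying need is constant. If every fall is counted, some participants will show one by chance, and about as many may show a rise. The plan counts the first group and not the second. For platelets, the window that decides who enters the table also supplies the baseline value. Zero is therefore excluded at baseline but allowed later, which tilts the comparison towards falls.

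The trial has one arm, so no control group shows what rate to expect without benefit. A reader of a row headed transfusion decrease, presented as support for efficacy, could credit the regimen with a figure that unchanged need would also produce. Baseline-independent participants who begin to need transfusion are outside these tables altogether.

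**Working it through.** The documents give no expected value for this measure and no transfusion rate or distribution, so there is no stated figure to reproduce. The check asks what the definition returns when need does not change.

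**Set-up.** Let X be a participant's count in the baseline window and Y the count in a later window of equal length, independent and with the same mean m. From the plan: a decrease is Y < X (this includes Y = 0), and entry requires X ≥ 1. Assumed: Poisson counts, and the values of m.

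**Formula.** Before selection, falls and rises are equally likely, so P(Y<X) = [1 − P(X=Y)]/2. A fall implies X ≥ 1, so after selection P(decrease) = P(Y<X) / (1 − e^−m).

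- m = 1: 34.6% / 63.2% = 54.7%
- m = 4: 42.8% / 98.2% = 43.6%

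**Poisson results, in per cent (computed from unrounded values).**

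| Mean per window | Share with X ≥ 1 | Decrease, no selection | Decrease, given X ≥ 1 | Unchanged | Increased |
|---|---|---|---|---|---|
| 1 | 63.2 | 34.6 | 54.7 | 27.4 | 17.9 |
| 2 | 86.5 | 39.6 | 45.9 | 21.8 | 32.3 |
| 4 | 98.2 | 42.8 | 43.6 | 14.6 | 41.8 |
| 8 | 100.0 | 45.0 | 45.0 | 10.1 | 45.0 |

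Selection adds 54.7 − 34.6 = 20.1 points at mean 1, but only 43.6 − 42.8 = 0.8 points at mean 4. At mean 4 the planned row would show about 44% decreased and leave out about 42% increased.

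**Other no-change patterns, share labelled decreased.**

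| Pattern | Range |
|---|---|
| Poisson, mean 0.5 | 67.9% |
| Poisson with gamma variation between participants, means 1–8 | 45–55% |
| Overdispersed within participant (variance 1.5 to 3 times the mean), means 1–8 | 46–73% |
| Compared in units, 1 or 2 per transfusion at random, means 1–8 | 46–60% |
| Regular: 2, 4 or 8 occasions, each used with probability 0.5–0.9 | 16–40% |

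**Units or frequency.** At Poisson mean 1, the share is 54.7% on frequency, 60.2% on units, and 61.9% if a fall in either is enough. The unspecified comparison therefore moves the result.

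**The 50% row.** Compared in units under the same no-change model, it is met by 54.4%, 36.9%, 22.7% and 12.0% at means 1, 2, 4 and 8. It is less exposed to chance at higher rates, but not at low ones.

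**Red cells.** Dependence looks back 60 days, while the baseline window is 8 × 7 = 56 days. A participant transfused only on days 57 to 60 before Day 1 enters with a baseline of zero. The exclusion of zero is exact for platelets and approximate for red cells.

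**Later visits.** Protocol 6.2.1 and 8.3 end transfusion recording with eltrombopag for participants who stop it because of Week 26 non-response, relapse or alternative treatment. The SAPs do not say how these participants are counted afterwards. Being transfusion-free counts as a decrease, so an unrecorded window could be programmed as one.

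**The case against.** The strongest reply is that the row does not stand alone. It sits beside the 50% row and full group summaries of frequency and units for the same participants, so a net rise would be visible. Other outputs cover part of the gap: the transfusion-free interval at Weeks 13 and 26 is not limited to baseline-dependent participants, and renewed transfusion in a transfusion-independent responder is a relapse criterion. The measure is descriptive, lies outside the protocol's own transfusion endpoints (interval and independence), and no formal testing is planned even for the primary endpoint. The size of the chance rate also rests on assumed distributions. Protocol 6.2.1 describes transfusion guided by count thresholds, which may be more regular than Poisson and would favour the lower end of the range.

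Most of this stands, and it makes the point minor. It does not remove it. Group means, medians and extremes do not say how many individuals rose, and the relapse rule and transfusion-free interval do not supply that count. Uncertainty about the chance rate is itself a reason to print the increases, because they would show the background variation directly.

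**Conclusion.** The point holds as a minor one. The measure counts only favourable movement per participant, from one baseline window, in a group chosen for having been transfused. With unchanged need, about 44–55% would be labelled decreased if counts are independent Poisson with mean 1 to 8 per window, and roughly 16–73% under the other patterns tried. These are not hard limits: perfectly constant counts would give no decreases at all. A reported rate in the 40s or 50s would be compatible with no change in need.

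Four stronger readings are tempting, and the documents do not support them.

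- A reader might infer that increases never show. A net rise would appear in the group summaries; only the per-participant count is missing.
- A reader might take 44–55% as a property of this plan. It depends on an assumed distribution and assumed means.
- A reader might blame baseline selection throughout. It matters mainly at low rates; at mean 4 and above the issue is almost entirely one-sided counting.
- A reader might convert the percentages into a head count. The documents do not say how many participants are transfusion-dependent, and at Week 52 and later recording has already ended for some.

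The measure entered the primary-analysis SAP on 1 July 2022, after enrolment was complete in an open-label trial but before database lock. Nothing in the documents shows that it was chosen with results in view.

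**What to change.** In Sections 2.7.1 to 2.7.3:

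1. State whether a decrease is judged on number of transfusions or on units.
2. In one table, for the same participants and window, report decreased, unchanged and increased for platelets and for RBC, with the median paired change from baseline. A confidence interval is optional. Keep the transfusion-free and 50% rows as descriptive companions.
3. Add the number of baseline-independent participants transfused in each window.
4. Count only participants whose transfusions were still being recorded in that window, and print how many were not. The exclusions fall on non-responders and relapsers, so the shrinking denominator should be visible.

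All of this uses data already collected. The cost is some SAP wording, a few extra rows, and a less favourable picture for a descriptive, untested measure.
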